6.2 RPC1063

RPC1063 (also known as ozanimod or BMS-986374) is a small molecule compound that selectively and potently activates the sphingosine-1-phosphate 1 receptor (S1P1) and the S1P 5 receptor (S1P5), although it is more selective towards S1P1 over S1P5. In vitro, RPC1063 has little activity on the other sphingosine-1-phosphate (S1P) receptors, showing half maximal effective concentration (EC50) greater than 10,000 nM for S1P2, > 5000 nM for S1P3, and > 2000 nM for S1P4. RPC1063 is extensively metabolized in humans with up to 13 metabolites identified in plasma, urine, and feces, including 2 active selective major metabolites and one inactive major metabolite found in human plasma at steady state. The 2 active metabolites (CC112273 and CC1084037) have similar structures to ozanimod and similar selectivity across the S1P receptor family.

Many cell types express S1P₁, including vascular endothelial cells, brain cells, and lymphocytes (Rosen et al, 2009). Stimulation (agonism) of this receptor results in biological activities that includes lymphocyte retention in peripheral lymphoid organs (eg, lymph nodes and gastrointestinal Peyer's patches), resulting in reversible systemic reduction in circulating lymphocytes (Mandala et al, 2002). Given the immune dysregulation observed in UC (Ordas et al, 2012), prevention of

trafficking of disease-exacerbating, self-reactive lymphocytes to the gut is likely to have salutary immunomodulatory effects with a consequent dampening of disease processes.

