10.3 Selection of Dose in the Trial

The dose of RPC1063 1 mg once each day was based on the completed Phase 1 (RPCS-001 and RPC01-102) and Phase 2 (RPC01-202) and Phase 2/3 (RPC01-201) trials (see [Section 6.2.2](#) and subsections). The 1 mg/day dose demonstrated better efficacy than the [REDACTED] mg/day dose across various clinical and endoscopic endpoints in these clinical trials. Furthermore, the expected magnitude of the pharmacodynamic effect on peripheral lymphocyte reduction was observed and this dose demonstrated an acceptable safety profile.

A dose escalation over the first 7 days ([REDACTED] mg/day on Days [REDACTED] and [REDACTED] mg/day on Days [REDACTED]) will be implemented, as results from the Phase 1 study (RPCS 001) and preliminary results from the Phase 2 study (RPC01-202) indicate that use of a dose escalation regimen appears to mitigate the magnitude of reduction in heart rate (HR). Preliminary evidence from these studies suggested that patients who increase their dose progressively over the first week are less likely to have a profound decrease in HR or blood pressure; therefore, a dose escalation starting with [REDACTED] mg RPC1063 for the first 4 days of dosing followed by [REDACTED] mg on Days [REDACTED] before progressing to the 1 mg/day dose will be used.

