13.1.11 Clinical Laboratory Evaluations

The central laboratory will analyze the samples. Further details of the procedures to be followed for sample collection, storage, and shipment will be documented in a laboratory manual.

Additional and repeat laboratory safety testing may be performed at the discretion of the Investigator and analyzed by the local laboratory. Approval from the Medical Monitor must be obtained if any lab test is required to be repeated > 2 times.

- Hematology: Red blood cell count, total and differential WBC count (basophils, eosinophils, lymphocytes, monocytes, and neutrophils), platelet count, hemoglobin (Hb), hematocrit, mean corpuscular volume, mean corpuscular hemoglobin, and mean corpuscular hemoglobin concentration. Total WBC count and all differential WBC counts will not be disclosed for Visit █ only and will be monitored centrally throughout the trial.

- Chemistry:
 - Full chemistry panel at Baseline: sodium, potassium, chloride, calcium, magnesium, phosphate, blood urea nitrogen, glucose, HbA1c, albumin, alkaline phosphatase, creatinine, ALT, AST, gamma glutamyl transferase (GGT), total bilirubin, conjugated bilirubin, total cholesterol, triglycerides, high-density lipoprotein, low-density lipoprotein, and [REDACTED].
 - ◆ HbA1c will be repeated annually
 - All other visits – blood urea nitrogen, albumin, alkaline phosphatase, creatinine, ALT, AST, GGT, total bilirubin, conjugated bilirubin, [REDACTED]. Of note, [REDACTED] will not be disclosed for Visit [REDACTED] to maintain the blind from the parent trial from which a patient may be entering.
- Urinalysis: Leukocytes, specific gravity, bilirubin, blood, glucose, ketones, pH, protein, and urobilinogen
[REDACTED]
- The central laboratory will analyze routine [REDACTED]. Details regarding collection of samples, shipment of samples, reporting of results, laboratory reference ranges, and alerting abnormal values will be supplied to the site before site initiation in a trial laboratory manual. The results of the analysis will be made available to each site by the central laboratory.
- Investigators will be asked to comment on those abnormalities on the respective laboratory result page, including a notation of the clinical significance of each abnormal finding in the patient's source documents. The laboratory sheets will be filed with the patient's source documents.

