14.2 Statistical Methods

14.2.1 General Considerations

All efficacy and safety data will be listed by patient. Baseline is defined as the last observed measurement prior to the Day █ receipt of investigational drug.

In general, descriptive summaries will be presented for the efficacy and safety variables collected. Continuous variables will be summarized using number of patients (n), mean, standard deviation (SD), minimum, median, and maximum. Categorical variables will be summarized using frequency counts and percentages.

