14.5 Safety Analyses

Adverse events will be monitored during the trial and the data analyzed with respect to incidence within each parent trial treatment group as well as severity and potential relationship of the AEs to investigational drug.

All AEs with a start date before the first dose date in RPC01-3102, which are ongoing from a previous trial to RPC01-3102, will be listed in the AE data listing and labeled as “Prior Adverse Event.”

Adverse events with an onset date on or after the first open-label dose date in RPC01-3102, or with onset prior to the first open-label dose date in RPC01-3102 that increase in severity on or after the first dose of investigational drug will be considered treatment emergent. Treatment-emergent AEs will be summarized for the Safety population by System Organ Class and Preferred Term and presented in descending order of frequency within each System Organ Class. Serious AEs and AEs leading to discontinuation will be summarized similarly.

Associated laboratory parameters such as hepatic profile, renal function, and hematology values will be grouped and presented together. For each laboratory test, individual patient values outside the standard reference range will be flagged and listed. Shift tables will be produced showing the frequency of shifts from Baseline to the highest and to the lowest on-trial value in and out of the normal range as well as by visit. Changes from Baseline to each visit for each numeric laboratory parameter will also be summarized.

The change from Baseline to each visit for each of the vital sign variables will be summarized. Abnormal vital sign values will be flagged and listed.

The change from Baseline to each visit for each of the ECG parameters will be summarized. An outlier analysis of ECG results will be conducted.

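### Laboratory, vital-sign and ECG change is measured from an on-drug Baseline in patients who enter already taking ozanimod, with no planned split by parent treatment and no pre-ozanimod comparison

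*Combined protocol and SAP*

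**What the plan says.** Section 14.2.1 has a single sentence for efficacy and safety data alike: "Baseline is defined as the last observed measurement prior to the Day", followed by a blacked-out day number and the receipt of investigational drug. It names no trial.

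Section 14.5 builds its numeric safety summaries on that Baseline. For laboratory data, "Shift tables will be produced showing the frequency of shifts from Baseline to the highest and to the lowest on-trial value", and also by visit; in addition, "Changes from Baseline to each visit for each numeric laboratory parameter will also be summarized". For vital signs, "The change from Baseline to each visit for each of the vital sign variables will be summarized". ECG parameters are handled the same way. The section says that adverse-event incidence is examined within parent-trial treatment groups. It states no grouping for laboratory, vital-sign or ECG summaries.

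Some displays do not depend on Baseline. Section 14.5 flags and lists out-of-range laboratory values and abnormal vital signs and plans an ECG outlier analysis. The synopsis adds tabulated incidence of abnormal vital signs and ECG outliers.

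On the drug, section 6.2 describes S1P1 agonism as "resulting in reversible systemic reduction in circulating lymphocytes". On entry values, section 13.1.11 says: "Total WBC count and all differential WBC counts will not be disclosed for Visit █ only and will be monitored centrally throughout the trial". Section 10.8 lists leukocytes among the laboratory values handled so as to protect the parent-trial blind.

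**The concern.** Change from Baseline describes a drug's effect on a laboratory value only if Baseline was measured off the drug. In an extension that some patients enter on treatment, a Baseline at entry measures drift after the effect has occurred. A patient whose lymphocytes fell below range in the parent trial and stayed there contributes near-zero change and no normal-to-low shift. A patient first exposed here contributes the full fall. If the two are summarized together, the result depends on the mix of prior treatment.

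Long-term safety is the first objective in section 7.1. The RPC01-202 entrants have at least one year of open-label treatment before entry, so they bear most directly on that objective. They would also show the least change in these summaries.

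**Working it through.** **Which Baseline.** Section 14.2.1 does not name the trial. Elsewhere the current text uses the word for this extension:
- Sections 8.1 and 8.3.2 judge clinical improvement from the RPC01-3102 Baseline Visit.
- Section 13.1.11 schedules a full chemistry panel at Baseline. It asks for a serum pregnancy test at Baseline depending on the time since the last one in the parent trial, so the two are distinct.
- Section 14.5 dates treatment emergence from the first RPC01-3102 dose.

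Extension entry is therefore the natural reading. One item of amendment history (version 2.0 to 3.0), about missing data, counts parent-study values as post-baseline. It is not current text, but it shows that the reference point needs stating.

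**Who is on drug at entry.** Section 9.1 requires RPC01-202 entrants to have completed at least 1 year of the open-label period, and section 10.1 keeps them on 1 mg. Under Table 2 footnotes a and b, the last parent visit generally serves as the first visit here, and parent drug is withheld only until that visit. No washout is planned. The synopsis treats an open-label part of RPC01-3101 in the same way, but the text is partly blacked out. No count is given.

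**Whether entry values carry drug effect.** For leukocytes the protocol implies that they can: it withholds them at one visit to protect the parent blind, and section 6.2 describes the lymphocyte reduction.

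**Whether another summary supplies the missing comparison.** Section 14.3 summarizes characteristics from the previous trial, but lists disease history, prior treatment and Mayo items. No pre-ozanimod laboratory, vital-sign or ECG value is used.

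**Size, mean change.** The plan states no figure to reproduce. Let f be the share at full, steady effect D at entry, with zero further change; the rest have no effect at entry and reach D on trial.

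Pooled mean change = f × 0 + (1−f) × D = (1−f)D.

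- f = 0.25: 0.75 D
- f = 0.50: 0.50 D
- f = 0.75: 0.25 D
- f = 1 (on-drug entrants shown alone): 0

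**Size, shift table.** Assume a share a of patients is below range off drug and b on drug. With an off-drug Baseline, the normal-to-low share of all patients is (1−a)b, taking pre-drug and on-drug status as independent. With an on-drug Baseline it is 0 if low status persists, or (1−b)b if status is independent between visits. The pooled share weights these by 1−f and f. For a = 5%, b = 50%:
- Off-drug Baseline: 0.95 × 0.50 = 47.5%.
- Pooled, f = 0.50, persistent: 0.50 × 47.5% = 23.75%.
- Pooled, f = 0.50, independent: 0.50 × 25% + 0.50 × 47.5% = 36.25%.

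| a, b (assumed) | Off-drug Baseline | Pooled, persistent (f = 0.25 / 0.50 / 0.75) | Pooled, independent (f = 0.25 / 0.50 / 0.75) |
|---|---|---|---|
| 2%, 20% | 19.6% | 14.7 / 9.8 / 4.9% | 18.7 / 17.8 / 16.9% |
| 5%, 50% | 47.5% | 35.6 / 23.8 / 11.9% | 41.9 / 36.3 / 30.6% |
| 10%, 70% | 63.0% | 47.3 / 31.5 / 15.8% | 52.5 / 42.0 / 31.5% |

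**What stays visible.** In the middle row with f = 0.50 and persistent status, the low-to-low cell holds 0.50 × 50% + 0.50 × 5% × 50% = 26.25%. Added to the 23.75% normal-to-low, this gives 50%, which is b. The total below range does not depend on Baseline; only its attribution to the period on drug is lost.

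**With a pre-ozanimod Baseline.** Under the same assumptions, mean change returns to D and the middle-row normal-to-low share to 47.5%, whatever f is.

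**The case against.** The strongest reply is that change since extension entry answers a proper question for an uncontrolled, descriptive extension: what happens with continued treatment. That stands. It is a reason to keep entry Baseline, not a reason to omit the other comparison.

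Several stronger readings are tempting and are not supported:

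- A reader might infer that the tables conceal the drug's effect. They do not. Low-to-low is a cell of the shift table, out-of-range values are flagged and listed, white-cell counts are centrally monitored, and abnormal vital signs and ECG outliers are tabulated. Patients first exposed here still show the effect. Listings give no group estimate, however, and a low-to-low cell does not show that the low value arose on ozanimod.
- A reader might infer that pooling is planned. Section 14.5 is an outline and does not say so; it gives a split for adverse events and is silent on the rest.
- A reader might infer a sustained heart-rate or ECG effect at entry. Section 10.3 ties the heart-rate reduction to starting treatment, and nothing in the documents shows an ECG effect carried into entry. Lymphocytes carry the argument.
- A reader might treat this as separate from the efficacy baseline. One sentence in 14.2.1 governs both, so amending it affects both unless the amendment is limited by data type.
- A reader might want a table of events labelled as prior adverse events. Events that began earlier and did not worsen are not new in this trial, and they are listed; worsened ones count as treatment-emergent. A further table is preference.

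**Conclusion.** The point holds in limited form. On the natural reading of 14.2.1, at least all RPC01-202 open-label entrants have an on-drug Baseline, and 14.5 plans neither a parent-treatment split nor a pre-ozanimod comparison for laboratory, vital-sign and ECG data. Change and shift summaries then omit effects already present in these patients and, if groups are combined, dilute them by about the factor 1−f. The practical weight falls on lymphocytes and other hematology values.

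The size cannot be fixed from the documents. The number on drug at entry, D, a and b are all absent, so the figures above are illustrations. They also assume full, steady effect at entry in the treated group and none in the others; partial effect or further change would move the results. If the sponsor intended a parent-trial Baseline, the omission disappears for patients whose parent Baseline preceded RPC1063, but 14.2.1 still has to say so.

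**What to change.** In section 14.2.1, name the trial whose first dose sets Baseline for laboratory, vital-sign and ECG data, and say whether the same rule applies to efficacy, so that one edit does not change both by accident.

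In section 14.5:
1. Present laboratory, vital-sign and ECG change and shift summaries by parent-trial treatment group, as is already stated for adverse events.
2. Keep the summaries from entry Baseline.
3. For patients already treated, add change and shift from the last value before the first RPC1063 dose in any trial, taken from the parent database. Do this at least for hematology.

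This needs no new visit, sample or procedure. The cost is more tables and a merge of parent-trial laboratory records, plus vital-sign and ECG records if the addition is extended to them. Section 14.3 already draws on previous-trial data, so linkage to the parent trials is needed in any case.

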14.6 Interim Analyses

Interim analyses were performed to support regulatory submission activities for the MS and UC indications.

15 DIRECT ACCESS TO SOURCE DATA/DOCUMENTS

15.1 Monitoring

The Sponsor has engaged the services of a CRO to perform all monitoring functions within this clinical trial. The CRO monitors will work in accordance with CRO standard operating procedures (SOPs) and have the same rights and responsibilities as monitors from the Sponsor organization. Monitors will establish and maintain regular contact with the Investigator.

Monitoring visits will be conducted according to all applicable regulatory requirements and standards. Regular monitoring visits will be made to each site while patients are enrolled in the trial.

15.2 Data Management/Coding

Electronic Data Capture (EDC) will be used for this trial, meaning that all eCRF data will be entered in electronic forms at the site. All EDC systems used in the trial will have access-controlled security and an audit history available to document any changes made to the data throughout the course of the trial. Data collection recorded in site source documents will be entered into the eCRF by authorized site staff designated by the Investigator. Patients will record whether they took the daily dose of investigational drug directly into an electronic diary, and this will be considered a source document. Appropriate training and security measures will be completed with the Investigator, all authorized site staff, and patients prior to the trial being initiated and any data being entered into the system for and/or by any trial patients.

All data entered by the site staff must be entered in English. The eCRFs should be completed contemporaneous to the patient's visit. The Investigator may delegate data entry, but is responsible for verifying that all data entries in the eCRFs are accurate and correct at the conclusion of the trial.

Source documents are all documents used by the Investigator or hospital that relate to the patient's medical history, that verify the existence of the patient, the inclusion and exclusion criteria, and all records covering the patient's participation in the trial. They include laboratory notes, ECG results, memoranda, pharmacy dispensing records, patient files, etc.

Source documents will be made available for inspection by the trial monitor at each monitoring visit. The Investigator must complete eCRFs for each patient who receives investigational drug. Any copy of source document(s) that are provided to the Sponsor or its representatives for any purpose (eg, in support of an SAE report) must be redacted such that all patient-identifying information is removed, and clearly labeled with the trial and patient number.

All AEs and medical histories recorded in the eCRF will be coded using the Medical Dictionary for Regulatory Activities (MedDRA). Concomitant medications will be coded using the World Health Organization (WHO) drug dictionary. Versions of dictionaries to be used will be specified in the data management plan for the trial.

15.3 Quality Assurance and Inspections

Sites, the trial database, and trial documentation may be subject to Quality Assurance audit during the course of the trial by the Sponsor or CRO on behalf of the Sponsor. In addition, inspections may be conducted by regulatory bodies at their discretion.

16 QUALITY CONTROL AND QUALITY ASSURANCE

16.1 Study Monitoring and Source Data Verification

According to the Guidelines of Good Clinical Practice (CPMP/ICH/135/95), the Sponsor is responsible for implementing and maintaining quality assurance and quality control systems with written SOPs. Study Monitoring including, risk-based monitoring, risk management and mitigation strategies as well as analytical risk-based monitoring, responsibilities, and requirements, including handling of noncompliance issues and monitoring techniques (central, remote, or on-site monitoring) will be followed as per the monitoring plan.

Quality control will be applied to each stage of data handling.

The following steps will be taken to ensure the accuracy, consistency, completeness, and reliability of the data:

- Investigator meeting(s)
- Central laboratories for clinical laboratory parameters and ECGs
- Site initiation visit
- Early site visits post-enrollment
- Routine site monitoring
- Ongoing site communication and training
- Data management quality control checks
- Continuous data acquisition and cleaning
- Internal review of data
- Quality control check of the final clinical study report

In addition, Sponsor and/or CRO Clinical Quality Assurance Department may conduct periodic audits of the trial processes, including, but not limited to site facilities, central laboratories, vendors, clinical database, and final clinical study report. When audits are conducted, access must be authorized for all trial-related documents including medical history and concomitant medication documentation to authorized Sponsor's representatives and regulatory authorities.

16.2 Investigational Medicinal Product Quality Issues

Investigational Medicinal Product Quality Issues such as IP safety, purity, potency, quality and identity (eg, evidence of suspected tampering of product) must be reported as soon as possible to the study Clinical Trial Monitor and/or Clinical Trial Manager or designee. Report any issue or concern of all sponsor-supplied IP (eg, manufacturing, packaging and labelling, storage, and/or distribution), if suspected to have occurred before the product was received, becomes the responsibility of the investigational site. This includes suspected quality issues of components co-packaged with the drug, labelling, and IP device/drug combination products, and medical devices.

- In the event of a suspected product quality issue, the immediate action to be taken by site is to quarantine the affected product. Do not dispose of the product unless retention presents a risk to personnel (eg, cytotoxic, risk of injury from broken glass or sharps).

- When reporting, provide as much product information as possible. Suspected IP quality issues will be investigated, and a response will be provided back to the investigational site.

17 ETHICS

17.1 Institutional Review Board or Independent Ethics Committee

An IEC should approve the final protocol, including the final version of the Informed Consent Form (ICF), and any other written information and/or materials to be provided to the patients. The Investigator will provide the Sponsor or CRO with documentation of IRB/IEC approval of the protocol and ICF before the trial may begin at the site(s). The Investigator should submit the written approval to the Sponsor or representative before enrollment of any patient into the trial.

The Sponsor or representative should approve any modifications to the ICF that are needed to meet local requirements.

The Investigator will supply documentation to the Sponsor or CRO of required IRB/IEC's annual renewal of the protocol, and any approvals of revisions to the ICF document or amendments to the protocol.

The Investigator will report promptly to the IRB/IEC, any new information that may adversely affect the safety of patients or the conduct of the trial. Similarly, the Investigator will submit written summaries of the trial status to the IRB/IEC annually, or more frequently if requested by the IRB/IEC. Upon completion of the trial, the Investigator will provide the Ethics Committee with a brief report of the outcome of the trial, if required.

